3.3 Benefit/Risk Assessment

Based on information about relamorelin obtained to date, the benefits of study participation are expected to include accelerated GE and clinically meaningful improvement in the symptoms of DG, including nausea, abdominal pain, postprandial fullness, bloating, vomiting frequency, early satiety, and vomiting severity. A potential risk of treatment is worsening of glycemic control, including the possibility of diabetic ketoacidosis occurring. However, preventive measures, including special laboratory assessments to allow early recognition by investigators and participants of rising glucose levels, are being included in this protocol so that early remedial action (eg, adjustment of medication and diet) may be taken to minimize increase in glucose levels; this might increase the incidence of hypoglycemic reactions, especially in participants with T1DM. See Section 5, Study Design for details of study procedures, dose, and study design justification.

More detailed information about the known and expected benefits and risks and reasonably expected AEs associated with relamorelin treatment may be found in the investigator’s brochure (Relamorelin Investigator’s Brochure); information about the investigational directions for use for the pen injector, the device that will be used to administer study treatment are also provided.

4 Objectives and Endpoints

Key Objectives	Key Endpoints

 • To compare the efficacy of relamorelin with that of placebo in participants with DG with respect to a composite of the following core signs and symptoms of DG: 
 ○ Nausea ○ Abdominal pain ○ Postprandial fullness ○ Bloating • To compare the safety of relamorelin with that of placebo in participants with DG 	
 • Change from baseline to Week 12 in the weekly DGSSS • Change from baseline to Week 52 in weekly average DGSSS • AEs, clinical laboratory values, vital signs, ECGs, HbA1c, and anti-relamorelin antibodies

4.1 Clinical Hypotheses

The clinical hypotheses are:

DG participants receiving relamorelin compared to DG participants receiving placebo will experience greater improvement in DGSSS as measured by:

- The change from baseline to Week 12 weekly DGSSS, and
- The change from baseline to Week 52 weekly average DGSSS (defined as the average of the 4 weekly DGSSS from the 4 weeks prior to the Week 52 visit).

Baseline is defined as the average of the 2 average DGSSS from the 2-week placebo Run-in Period.

[figure not shown]
5 Study Design

5.1 Overall Design

- Global, multicenter, randomized, double-blind, placebo-controlled, parallel-group
- Treatment Groups: Relamorelin 10 µg and placebo; BID, SC
- Study Duration: 52-week Treatment Period.

See [Figure 5-1](#) for a Study Schematic.

Figure 5-1 RLM-MD-04 Study Schematic

Study Population:

Two different groups of participants may enter into the study:

- Participants who met all Screening and Run-in Period criteria in lead-in Study RLM-MD-01 or lead-in Study RLM-MD-02 (including compliance with dosing and data entry into the DGSSD during the lead-in study Run-in Period), but were not randomization-eligible at the end of the lead-in study Run-in Period, are eligible for randomization in Study RLM-MD-04 if:

- They had no vomiting episodes recorded in the DGSSD and had an average daily DGSSS ≥ 12 at the end of the lead-in study Run-in Period.

OR

- They had vomiting episodes recorded in the DGSSD but had an average daily DGSSS of ≥ 12 and < 16 at the end of the lead-in study Run-in Period.

In the current study, these “**rollover participants**” will enter the study at Visit 1 (Randomization); they will not undergo Screening (Visit -2) or the Run-in Visit (Visit -1) procedures

2. Patients who undergo screening and run-in procedures in Study RLM-MD-04 are “**de novo participants**”. To be eligible for randomization in the current study, de novo participants must meet all Screening and Run-in Period criteria for Study RLM-MD-04, including:
 - a. At Screening, be male or female age 18 years and older; T1DM or T2DM with controlled and stable blood glucose levels and HbA1c \leq 11%; symptoms suggestive of DG for at least 3 months (one of which must be nausea), with mechanical obstruction of the GI tract as the cause of symptoms having been ruled out.
 - b. History of nausea and/or at most a single episode of vomiting in the 2 weeks prior to Screening (Visit -2), as ascertained by participant history
 - c. During the Run-in Period, delayed GE by gastric emptying breath test (GEBT)
 - d. After Run-in Period: Evidence of compliance during the Run-in Period with the use of the electronic hand-held device for entry of data, with twice daily SC injections of the study treatment, and no treatment with GI promotility agents; a score of \geq 12 for the average of the daily DGSSS measured during the Run-in Period.

For studies conducted at US (IND) sites and non-US (non-IND) sites, data from IND and non-IND study sites will be pooled together for analysis.

5.2 Participant and Study Completion

Approximately 5000 participants will be screened in lead-in Studies RLM-MD-01 and RLM-MD-02. Certain participants who were not eligible for randomization at the end of the lead-in study Run-in Period (rollover participants) may enter this study (see Section 5.1 for rollover participant eligibility criteria).

In addition, participants who undergo Screening and Run-in Visit procedures will be eligible for randomization if they meet all inclusion/exclusion criteria for the current study (see Sections 6.1.2 and 6.2.3 for de novo participant eligibility criteria).

The goal is to achieve 600 participants assigned to study treatment (400 to relamorelin and 200 to placebo). A total of 300 participants are expected to complete the study (200 treated with relamorelin and 100 with placebo). See Section 10.1 for details on sample size determination.

5.3 End of Study Definition

The end of the study is defined as the date of the last visit of the last participant in the study.

A participant is considered to have completed the study if he/she has completed at least 364 days of treatment, and the last visit (Visit 7). Independent of the end of study definition, all laboratory tests with values considered clinically significantly abnormal during participation in the study or within 30 days after the last dose of study treatment should be repeated until the values return to normal or baseline or are no longer considered clinically significant by the investigator or medical safety physician (MSP).

5.4 Scientific Rationale for Study Design

The sponsor has designed this randomized, double-blind, placebo-controlled, parallel-group study to follow regulatory recommendations for conduct of Phase 3 therapeutic confirmatory studies, specifically the ICH Harmonized Tripartite Guideline E8 (General Considerations for Clinical Trials, Current Step 4 version dated 20 July 2000) and Guideline E10 (Choice of Control Group and Related Issues in Clinical Trials, Current Step 4 version dated 17 July 1997). The study also has been designed to comply with recommendations made by the US FDA, Center for Drug Evaluation and Research (CDER) in the [Draft Guidance for Industry, Gastroparesis: Clinical Evaluation of Drugs for Treatment, July 2015](#), including those for the minimum duration of studies to show efficacy (at least 12 weeks) and for inclusion of a long-term placebo-controlled safety study (12 months, with appropriate pre-specified provisions for rescue medications) as part of the development plan.

Several design features have been incorporated in the current study in an effort to minimize bias, including double-blind design and random assignment of participants, helping to ensure that both known and unknown risk factors are distributed evenly between treatment groups. The use of a placebo control permits prospective comparison between the relamorelin group and the control group.

5.5 Justification for Dose

Study RM-131-009 was a 12-week Phase 2b, randomized, double-blind, placebo-controlled, parallel group study to evaluate the safety and efficacy of relamorelin in diabetic participants with moderate to severe DG. The doses included within the study were 10 µg BID, 30 µg BID, and 100 µg BID. In general, all doses tested within RM-131-009 appeared to demonstrate meaningful reductions in overall DG symptom scores including vomiting episodes, with acceptable safety and tolerability. The frequency of vomiting episodes was reduced from baseline over the 12-week treatment period to a similar extent for participants who received the 3 doses of relamorelin tested and placebo. Based upon the observed dose response of change-from-baseline symptom scores collected daily over the course of 12 weeks using the DGSSD, the 30 µg BID,

and 100 µg BID doses demonstrated apparent maximal symptom score improvements, while the 10 µg BID dose achieved near maximal improvements. Of note, the twice-a-day regimen of relamorelin appears to be necessary for effective symptom relief; the 10 µg once daily (QD) relamorelin did not demonstrate significant improvement in symptom relief compared to placebo after 28 days of dosing in Study RM-131-004.

Review of the safety laboratory data collected in RM-131-009 revealed an apparent dose-related increase in HbA1c values. Although the variability in HbA1c response was high across all treatments, the 30 µg BID and 100 µg BID doses demonstrated apparent maximal changes in HbA1c values, while the 10 µg BID dose resulted in an approximately half-maximal increase after 12 weeks of study. Shorter durations of treatment (4 weeks) with 10 µg BID of relamorelin, as observed in Study RM-131-004, did not demonstrate this apparent increase in HbA1c in diabetic participants.

Based on the efficacy and safety data, the relamorelin dose selected for this study is 10 µg BID.

6 Study Population

Prospective approval of protocol deviations to recruitment and enrollment criteria, also known as protocol waivers or exemptions, is not permitted.

6.1 Inclusion Criteria

6.1.1 Rollover Participants

Participants who were not randomization-eligible at the end of the Run-in Period of lead-in Studies RLM-MD-01 or RLM-MD-02 are eligible to be randomized in the study if all of the following criteria apply:

In the lead-in studies, participants must have met all Screening Visit and Run-in Period criteria for randomization into the Treatment Period (including compliance with dosing, entry of diary data into the DGSSD) except that:

1. They had zero vomiting episodes and an average daily DGSSS of ≥ 12 at the end of the lead-in study Run-in Period, as reported using the electronic hand-held device;

OR

2. They had vomiting episodes and an average daily DGSSS of ≥ 12 but < 16 at the end of the lead-in study Run-in Period, as reported using the electronic hand-held device.

6.1.2 De Novo Participants

Participants who undergo screening and run-in procedures for Study RLM-MD-04 are eligible to be included in the study if all of the following criteria apply:

1. Male or female participants aged 18 years or older at Screening (Visit –2)
2. T1DM or T2DM of at least 5 years' duration, with controlled and stable blood glucose levels (ie, no episodes of diabetic ketoacidosis, Hyperosmolar Hyperglycemic Nonketotic Diabetic Syndrome, or severe hypoglycemia within the 6 months preceding Screening [Visit –2])
3. HbA1c \leq 11.0% at Screening (Visit –2) in participants being treated with oral and/or parenteral medications for T1DM or T2DM with the goal of achieving controlled and stable glucose levels
4. DG defined as at least a 3-month history prior to Screening (Visit –2) of symptoms (one of which must be nausea) on an ongoing basis that are suggestive of GP (eg, nausea, abdominal pain, postprandial fullness, bloating, vomiting, and early satiety)
5. Female participants willing to minimize the risk of inducing pregnancy for the duration of the clinical study and Follow-up Period
A female participant is eligible to participate if she is not pregnant (has a negative urine pregnancy result prior to randomization; see [Appendix 5](#)), not breastfeeding, and at least one of the following conditions applies:
 - a. Not a woman of childbearing potential (WOCBP) as defined in [Appendix 5](#)
OR
 - b. A WOCBP who agrees to follow the contraceptive guidance in [Appendix 5](#) during the Treatment Period and for at least 7 days after the last dose of study treatment
6. Documentation of absence of an obstructing lesion on upper GI series with contrast or upper endoscopy, performed at some time before the Run-in period (Visit 2) but after the appearance of symptoms that led to the diagnosis of DG
7. Nausea and/or at most a single episode of vomiting during the 2 weeks prior to Screening (Visit –2), as ascertained by participant history
8. Delayed GE confirmed by abnormal GEBT, defined as GE half-time ($t_{1/2}$) \geq 79 minutes at the start of the placebo-controlled Run-in Period (Visit 2 of RLM-MD-01, RLM-MD-02, or this study). In countries where the GEBT is not available, delayed GE may be confirmed by abnormal scintigraphy result ($>$ 60% retention at 2 hours or $>$ 10% at 4 hours). Refer to the Study Reference Manual
9. The BMI criterion has been removed.
10. Able to provide written informed consent (IC) prior to any study procedures and willing and able to comply with study procedures
Additional inclusion criteria for randomization after the 2-week, placebo Run-in Period:
11. Compliance with the entry of data into the hand-held electronic device on at least 10 of 14 days during the Run-in Period

12. Compliance with administration of SC twice daily injections, as evidenced by entries made by the participant using the electronic, hand-held device on at least 10 of 14 days during the Run-in Period
13. The average of the daily DGSSS from the 2-week, Run-in Period must be ≥ 12

6.2 Exclusion Criteria

6.2.1 Both Rollover and De Novo Participants

1. Corrected QT Interval (QTc) > 470 msec in the absence of right or left bundle branch block, other intraventricular conduction delay (IVCD) with QRS duration > 120 msec, or paced beat on the ECG obtained at Screening (Visit 1).
2. Participants with a known allergy or hypersensitivity to the study treatments and their excipients (ie, mannitol or phenol)

6.2.2 Rollover Participants

Participants will be excluded from this study if any of the lead-in study exclusion criteria apply at Screening (Visit 1) and at the end of the Run-in Period (Visit 3) for randomization into the Treatment Period of Studies RLM-MD-01 and RLM-MD-02, except as specified in the inclusion criteria (Section 6.1).

6.2.3 De Novo Participants

1. Symptomatic Irritable Bowel Syndrome at Screening (Visit -2)
2. Small intestinal bacterial overgrowth (SIBO) at Screening (Visit -2)
3. History of anorexia nervosa, binge-eating, bulimia, or other eating disorder within 5 years of Screening (Visit -2)
4. History of intestinal malabsorption (including celiac disease even if well-controlled on a gluten-free diet) or pancreatic exocrine insufficiency; also, history of non-celiac gluten sensitivity
5. History of belching disorders, other nausea and vomiting disorders (eg, chronic nausea and vomiting syndrome, cyclic vomiting syndrome, cannabinoid hyperemesis syndrome), or rumination syndrome
6. History of chronic obstructive pulmonary disease or other causes of pulmonary dysfunction that have resulted in CO₂ retention
7. Gastric or duodenal ulcer within 3 months of Screening (Visit 1)

8. Evidence of hepatic disease defined as alanine aminotransferase (ALT) or aspartate aminotransferase (AST) $\geq 3 \times$ ULN, and/or direct bilirubin $\geq 2 \times$ ULN at Screening (Visit -2)
9. History of malignancy in the 3 years prior to Visit 1, except for adequately treated basal cell or squamous cell skin cancer, or in situ cervical cancer
10. Currently receiving parenteral feeding or presence of a nasogastric or other enteral tube for feeding or decompression
11. Use of metoclopramide, domperidone, prucalopride, macrolide antibiotics (eg, erythromycin, clarithromycin, azithromycin), or other drugs considered to be GI pro-motility agents (Table 7-2) for at least 10 days prior to the start of the Run-in Period (Visit -1)
12. Positive results on the urine drug screen at Screening (Visit -2). The sponsor may permit a participant with a positive urine drug screen (UDS) by immunoassay at Screening to continue in screening while confirmatory testing by a more specific method is carried out on an aliquot of the original urine sample. If the confirmatory test is negative, the initial positive UDS will be considered to have been a false-positive urine drug screen and the participant can continue in screening. Confirmatory testing will be done at the discretion of the sponsor and must be approved by the sponsor prior to analysis. The significance of a positive screen result for drugs prescribed for the participant (eg, barbiturates, benzodiazepines, amphetamines, but not opioids or cannabinoids) should be assessed by the Investigator as to whether their stable-dose usage is clinically appropriate, and, therefore, should not be exclusionary; use of these drugs on an as-needed basis is not allowed. See Section 6.4 for additional details regarding positive urine drug screen.
13. Currently taking opiates, or expecting to use opiates during the course of the clinical study. (see Section 7.7.1 for an exception to this prohibition)
14. Treatment with glucagon-like peptide-1 (GLP-1) agonist for at least 6 weeks prior to the start of the Run-in Period (Visit -1)
15. History of pyloric injection of botulinum toxin within 6 months of screening
16. History of gastric surgery such as fundoplication, gastrectomy, gastric pacemaker placement, vagotomy, or bariatric procedure (a history of diagnostic endoscopy is not exclusionary)
17. Randomization in any previous study in which relamorelin was a treatment
18. Estimated glomerular filtration rate (eGFR) of < 30 mL/min
19. Current enrollment in an investigational drug or device study or participation in such a study within 30 days of entry into this study
20. Allergic to, or intolerant of egg, wheat, milk, or algae, as these are components of the GEBT study meal

21. Females who are pregnant, nursing, or planning a pregnancy during the study. For females who are of childbearing potential, see [Appendix 5](#)
22. The participant has a condition or is in a situation which, in the investigator's opinion, may put the participant at significant risk, may confound the study results, or may interfere significantly with the participant's participation in the study
23. Participant is directly or indirectly involved in the conduct and administration of this study as an investigator, subinvestigator, study coordinator, other study staff member, or employee of Allergan, Inc.; or the participant is a first-degree family member, significant other, or relative residing with one of the above persons involved directly or indirectly in the study; or the participant is enrolled in this study at another clinical study site
24. Functional dyspepsia diagnosed before the diagnosis of diabetes mellitus
25. Hypersensitivity to the study treatments and their excipients (ie, mannitol or phenol)
26. Corrected QC Interval (QTc) > 470 msec in the absence of right or left bundle branch block, other intraventricular conduction delay (IVCD) with QRS duration > 120 msec, or paced beat on the ECG obtained at Screening (Visit 1)

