Approximately 5000 participants will be screened in lead-in Studies RLM-MD-01 and RLM-MD-02. Participants who do not meet certain randomization criteria may enter this study directly if they meet enrollment criteria defined below.

Study Population:

Two different groups of participants may enter the study:

- Participants who met all Screening and Run-in Period criteria in lead-in Study RLM-MD-01 or lead-in Study RLM-MD-02 (including compliance with dosing and data entry into the Diabetic Gastroparesis Symptom Severity Diary [DGSSD] during the lead-in study Run-in Period), but were not randomization-eligible at the end of the lead-in study Run-in Period, are eligible for randomization in Study RLM-MD-04 if:
 - They had no vomiting episodes recorded in the DGSSD and had an average daily DGSSS ≥ 12 at the end of the lead-in study Run-in Period.

OR

- They had vomiting episodes recorded in the DGSSD but had an average daily DGSSS of ≥ 12 and < 16 at the end of the lead-in study Run-in Period.

In the current study, these “**rollover participants**” will enter the study at Visit 1 (Randomization); they will not undergo Screening (Visit -2) or Run-in Visit (Visit -1) procedures.

2. Patients who undergo screening and run-in procedures in Study RLM-MD-04 are “**de novo participants**”. To be eligible for randomization in the current study, de novo participants must meet all Screening and Run-in Period criteria for Study RLM-MD-04, including:

At the Screening Visit (Visit -2):

- Male or female aged 18 years and older;
- T1DM or T2DM with controlled and stable blood glucose levels and HbA1c $\leq 11\%$;
- Symptoms suggestive of DG for at least 3 months (one of which must be nausea), with mechanical obstruction of the gastrointestinal (GI) tract as the cause of symptoms having been ruled out;
- History of nausea and/or at most a single episode of vomiting in the 2 weeks prior to Screening (Visit -2), as ascertained by participant history

[figure not shown]
At the End of the Run-in Period:

- Evidence of compliance during the Run-in Period with both the use of the electronic hand-held device for entry of data and with twice daily SC injections of the study treatment;
- No treatment with GI promotility agents during the Run-in Period;
- A score of ≥ 12 for the average of the daily DGSSS measured during the Run-in Period.

[figure not shown]
Number of Sites:

Approximately 700 sites globally (the combined number of sites from Studies RLM-MD-01 and RLM-MD-02).

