7.7.1 Prohibited Treatments and Washout Before the Study

The classes of drugs prohibited in the study are, with the exception SLGT-1 and SGLT-2 inhibitors, those that affect GI motility, either positively or negatively, and therefore could confound the assessment of the efficacy of study treatment on the signs and symptoms of DG. The SGLT-1 and SGLT-2 inhibitors are prohibited. Their mechanism of action is through causing increased glycosuria, which may affect interpretation of the GEBT results.

Table 7–2 provides a list of drug classes and treatments that are prohibited during this study and require washout during the Run-in Periods of the current study and the lead-in Studies (RLM-MD-01 or RLM-MD-02).

Table 7–2 Prohibited Medications and Washout Requirements

Drug Class/Treatment	Washout Required Prior to Baseline
Sodium-glucose co-transporter-2 (SGLT-1 or SGLT-2) inhibitors: Empagliflozin, canagliflozin, dapagliflozin, etc.	Prohibited only 3 days prior to the GEBT done in a subset of participants at a subset of sites at Visit 4 or the Early Termination Visit
Pro-motility agents: Metoclopramide, macrolide antibiotics (eg, erythromycin, clarithromycin, azithromycin), domperidone, prucalopride, or other drugs considered to be GI pro-motility agents	Rollover Participants: 10 days prior to the start of the Run-in Period of the Lead-in study De novo Participants: 10 days prior to the start of the Run-in Period of this study, RLM MD-04
Anticholinergics: Drugs with an anti-cholinergic mechanism of action as the basis of their therapeutic benefit, not those that have anti-cholinergic activity as a side effect	
Anti-emetics (Used for more than 1 day a week, or participant requires an anti-emetic drug once weekly repeatedly (ie, for 3 consecutive weeks or more), the investigator should contact the sponsor to discuss the safety of the participant continuing study treatment.)	
Amylin analogue: pramlintide	
5HT4 agonists (cisapride, tegaserod, and prucalopride)	
Opioids^a (eg, tramadol)	Washout period is not applicable as the use of opioids is not allowed. See Exclusion Criteria #12 and #13.
Glucagon-like peptide-1 (GLP-1) agonists: Exenatide, liraglutide, etc.	Rollover Participants: 6 weeks prior to the start of the Run-in Period of the Lead-in study De novo Participants: 6 weeks prior to the start of the Run-in Period of this study, RLM MD-04

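### De novo exclusions 11 and 14 state a minimum length of drug use, while Table 7-2 states the same periods as drug-free washouts

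*Protocol*

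**What the plan says.** **Exclusions.** In protocol Section 6.2.3, exclusion 11 covers use of metoclopramide, domperidone, prucalopride, macrolide antibiotics and other pro-motility drugs "for at least 10 days prior to the start of the Run-in Period". It cites Table 7-2, but for the list of drugs. Exclusion 14 reads "Treatment with glucagon-like peptide-1 (GLP-1) agonist for at least 6 weeks prior to the start of the Run-in Period".

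**Washout table.** Table 7-2 in Section 7.7.1 has a column for the washout required before baseline. For pro-motility agents it gives "De novo Participants: 10 days prior to the start of the Run-in Period of this study, RLM MD-04". For GLP-1 agonists in de novo participants it gives "6 weeks prior to the start of the Run-in Period of this study, RLM MD-04". The sentence introducing the table places the washout during the Run-in Periods, whereas these rows place it before Run-in starts.

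**Run-in condition.** The synopsis lists, among the conditions at the end of Run-in, "No treatment with GI promotility agents during the Run-in Period". Protocol Section 5.1 and SAP Section 4.1 carry the same condition. The post-Run-in randomization criteria in Section 6.1.2 (items 11 to 13) cover diary compliance, injection compliance and the DGSSS threshold, and omit it.

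**Status of the criteria.** Section 5.2 sends the reader to Sections 6.1.2 and 6.2.3 for de novo eligibility. The opening of Section 6 adds: "Prospective approval of protocol deviations to recruitment and enrollment criteria, also known as protocol waivers or exemptions, is not permitted".

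**The concern.** An exclusion criterion names the people to be kept out. Phrased as use for at least a given time, it keeps out people who took the drug that long. A washout rule keeps out people who took it recently. The two coincide only for some patterns of use. The wording looks like a statement of required non-use that was moved into an exclusion list without being inverted.

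Other items in the list do not have this problem. Exclusion 15, on pyloric botulinum toxin, uses *within* 6 months and agrees with its Table 7-2 row.

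What is at stake is the Run-in data. Section 7.7.1 says the prohibited motility-altering classes could confound the efficacy assessment, and Section 7.7.2 notes that some diabetic drugs in Table 7-2 delay gastric emptying. Delayed emptying at the start of Run-in is inclusion criterion 8. The Run-in DGSSS must average at least 12 for entry, and it is also the baseline for both key efficacy endpoints. Drug effect carried into Run-in could influence who qualifies and where the baseline sits.

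**Working it through.** The plan gives no figure to reproduce here, and no power or sample size calculation is involved. The check applies each text to the same patterns of use.

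**Inputs.** W is the stated period: 10 days for pro-motility agents (exclusion 11, Table 7-2) and 6 × 7 = 42 days for GLP-1 agonists (exclusion 14, Table 7-2). L is the length of a continuous course in days. g is the number of days from last dose to the start of Run-in.

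**Rules.**
- Table 7-2 (washout): barred if g ≤ W.
- Exclusion, reading A (a course of that length at any time before Run-in): excluded if L ≥ W.
- Exclusion, reading B (a course of that length running up to Run-in): excluded if L ≥ W and g ≤ 1.

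**Results.**

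| Pattern of use | Table 7-2 | Reading A | Reading B |
|---|---|---|---|
| Pro-motility, last dose the day before Run-in (g = 1), L = 1 to 9 | barred | not excluded | not excluded |
| GLP-1, g = 1, L = 1 to 41 | barred | not excluded | not excluded |
| Pro-motility, L = 10, stopped 11 days before | washout met | excluded | not excluded |
| GLP-1, L = 42, stopped 43 days before | washout met | excluded | not excluded |
| Either class, L = 90, stopped 5 days before | barred | excluded | not excluded |

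The first two rows are the gap for short courses running up to Run-in. Its upper ends are 10 − 1 = 9 and 42 − 1 = 41 days. Rows three and four show the mismatch in the other direction: reading A removes people who have completed the washout. The last row shows reading B missing a long-term user who stopped too recently for the table. Neither literal reading agrees with Table 7-2 throughout.

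**Which criterion is more exposed.** For pro-motility agents, the synopsis and Section 5.1 add a bar on use during Run-in. No Run-in randomization condition names GLP-1 agonists. Timing also differs. Appendix 9 gives a Screening Period of 4 weeks, or 28 days, so a 42-day window before Run-in reaches back at least 42 − 28 = 14 days before Screening begins. Compliance with the GLP-1 washout must therefore be judged partly from history, so the wording of exclusion 14 matters more.

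**If reconciled.** Once the exclusions and the table describe the same period of non-use, they classify every pattern above alike. No sample size or power figure changes.

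**The case against.** The strongest reply is that the protocol must be read as a whole. Table 7-2 is explicit that these periods are washouts, and Section 7.7.1 prohibits the listed classes during the study. A participant still taking a GLP-1 agonist at Run-in is barred whatever exclusion 14 says. Section 9 repeats that waivers are not allowed and calls adherence to the design requirements essential, which covers the table too. Exclusion 22 lets the investigator keep out anyone whose situation may confound the results. The intent is not in real doubt.

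All of that stands. A reader might infer that recent users are simply eligible, or that the protocol has no washout. The documents do not support either: the gap exists only if Section 6.2.3 is read alone. Nor do they show that sites decide from the criteria list without consulting Table 7-2.

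A reader might also infer that pro-motility use during Run-in is allowed because Section 6.1.2 is silent. It is not: the synopsis, Section 5.1 and SAP Section 4.1 make its absence a condition of randomization, so the omission is one of placement.

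Finally, a reader might infer bias in the comparison of relamorelin with placebo. Any carry-over into the baseline precedes blinded 2:1 allocation and is balanced between arms in expectation. Rollover participants follow the lead-in studies' criteria. SAP Sections 4.0 and 10.0 record early termination and limit the key efficacy endpoints to descriptive analysis.

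What the reply does not remove is that the list Section 5.2 points to for de novo eligibility contradicts the table, and that the table's introduction differs from its own rows on when the washout falls. The fallback text is therefore not fully consistent either.

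**Conclusion.** The point holds as an internal contradiction in an operative eligibility rule. Exclusions 11 and 14 describe duration of use, and Table 7-2 describes non-use over the same 10 days and 6 weeks.

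The gap of 1 to 9 days (pro-motility) or 1 to 41 days (GLP-1) assumes continuous use with a last dose the day before Run-in; other patterns give other mismatches, some of them over-exclusion. The number of participants concerned and the size of any effect on the breath test or DGSSS cannot be derived from the documents.

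The likely consequence is uneven enrolment decisions, a less well-defined de novo population, and some noise in the Run-in breath test and the DGSSS baseline. That baseline still enters the descriptive change-from-baseline results. No between-arm bias is shown. Exclusion 14 deserves attention first. Nothing here bears on which washout length is clinically right.

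**What to change.** Reconcile exclusions 11 and 14 with Table 7-2, and the table's introductory sentence with its rows, so that all describe the same period of non-use before Run-in. The content of that rule is for the sponsor to confirm. Repeat in Section 6.1.2, beside criteria 11 to 13, the Run-in condition on pro-motility agents already stated in the synopsis and Section 5.1.

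The cost is protocol wording only: no new assessment, no change to sample size and no change to the analysis. As the study has been terminated, new wording cannot alter who entered. The listing of prior and concomitant medications already planned in SAP Section 8.0 could show how many de novo participants are concerned, as far as those drugs were recorded.
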